## **Procedures**

Participants will be randomly assigned to Cognitive Behavioral Therapy in addition to standard routine care with the receiving of The Knee Book (Ministry of Health, 2013) or to standard routine care with The Knee Book provided after the written consent obtained and baseline questionnaire administered. Randomization using block randomization method will be implemented by an individual who is not involved in the recruitment process. Therefore, the allocation will be concealed in advance from the participants, researcher involved in recruitment, hospital staffs and therapists.

This research study will be suspended if more than 30 percent of the participants in treatment group show unexpected adverse event. The adverse event can be an increase in the knee pain intensity and emotional breakdown that will present before study enrollment. Serious adverse events were defined as death or admission to hospital, events attributable to the intervention, or events that caused unwarranted distress to a participant. However, the participants will be withdrawn from the study if any criminal illness detected which is non-identified psychiatric disorder. In addition, participants will be removed from the study if the female participant has

become pregnant during the study. The withdrawn participants will not be replaced in this study.

Participants do not have to stop taking medication which is prescribed by Orthopaedic doctor to participate in this study. There will be no rescue medication or procedure prepared but participants may contact with their medical professional in case of emergency. Participants will be asked for any discomfort symptoms along the study period.

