## **1.2 SIGNIFICANCE OF RESEARCH**

There are no risks for subjects on placebo. However, there is little risk in getting cognitive behavioral therapy. Patients may explore painful feelings, emotions and experiences. Besides, they may feel emotionally uncomfortable at times. They may cry, get upset or feel angry during a challenging session, or may also feel physically drained. However, the therapists will minimize any risks. The coping skills patients learn can help to manage and conquer negative feelings and fears.

The results of this study may provide some insights that may lead to better care for patients with recent onset chronic knee pain to enhance in managing pain. It may heightened the potential importance of cognitive behavioral intervention aiming to reduce levels of pain, functional disability, depressive and anxiety severity symptoms, pain catastrophising, fear- avoidance beliefs and increase levels of pain self- efficacy in the management of chronic knee pain patients. The study described in this study will determine comparative efficacy of these programs and the results will assist healthcare providers who are involved in the delivery of non- pharmacological interventions, researchers in the field of osteoarthritis, officials in healthcare governance and policy makers in planning for future arthritis self- management strategies, in order to effectively reduce health and economic burden of knee osteoarthritis.

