### **3.8 SAMPLING METHOD**

#### **Randomization and Masking**

The participants will be recruited from Hospital Putrajaya and Hospital Serdang. Participants will be identified from physician and from searches of patient records

that had consulted for knee pain problem within the period of February 2015 to July 2015. Patients will be invited to give consent to be contacted by staff nurse for the permission to review patients' medical records for a diagnosis of knee osteoarthritis. Patients of each recruitment site who were eligible will be contacted by researcher to enquire their willingness to participate in this research study. Potentially eligible patients will be invited to attend a face-to-face appointment with a researcher to discuss participating in the trial and to confirm their eligibility. Ineligible patients (and those who declined participation) will be referred back to their general practitioner. Those eligible patients who agreed to participate in this study will be in a list and numbered. The number in the name list of all eligible knee osteoarthritis patients who were agreed for the participation will be randomly chosen by using draw logs until 300 names been obtained from the list, in order to ensure that no bias will be involved in patient recruitment.

The selected 300 names from the sampling frame will be randomly allocated to either of the experimental or control group based on block randomization method by using random allocation software after the written consent obtained and baseline questionnaire administered. Then, the names will be divided into 13 smaller subgroups (eight to ten each subgroup) in each intervention and placebo group. All the names in the subgroups will be contacted personally before every assignment by a hospital staff who will be blinded to group allocation.

Because of the nature of the treatments, the participants or those providing the interventions to treatment assignment will be unable to mask. However, research assistants who obtained and assessed outcomes will be masked to assignment. Besides, the research assistants for treatment and control group are different. The research assistants then will submit the outcome measurements at each time measure to the researcher who is undertaking the analysis task.

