### 3.11 INTERVENTION PROTOCOL

Both the intervention and control group will receive standard routine care throughout the study. They have to attend clinic and physiotherapy session as usual on their fixed appointment date. However, the control group will be provided with The Knee Book (Ministry of Health, 2013) and not receive further intervention. Patients in the intervention group will be provided with The Knee Book (Ministry of Health, 2013) and to receive a three sessions of group Cognitive Behavioral Therapy (CBT) (each session will be last for two and a half hour) bi- weekly. The session will be held in a group of eight to ten patients and supervised by an experienced senior clinical psychologist ([name]) and a physiotherapist. The intervention will be delivered by physiotherapists and nurses who will receive at least one day of training specific to the trial from an experienced senior clinical psychologist with CBT experience. Each session will be audio- recorded with a written consent from the patients. Fidelity of the CBT session will be assessed for a random sample of recordings by the experienced psychologist with the Cognitive Therapy Rating Scale (Blackburn et al., 2000), which is a valid and reliable CBT rating scale. It has high internal reliability which is cronbach alpha 0.95 and good face validity. In addition, patients in the intervention group will assess the Client Satisfaction Questionnaire (CSQ-8) after the last session of group CBT received for measuring satisfaction with the therapy provided (Attkisson, 2012). It has high coefficient alpha (ranged from 0.83 to 0.93).

The outline of the Cognitive Behavioral Therapy module is prepared and modified based on Linton (2005). The CBT intervention will include an introduction, lecture (knowledge and insight), problem solving, skills training, homework assignments and a feedback of the session. An example of a knee OA patient will be applied throughout the intervention as a model for discussion and practice in problem solving, in order to enhance peer support and social bonding. Compliance with CBT is defined as attendance at the initial assessment and at least three subsequent sessions.

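### The serious adverse event definition makes any event caused by the intervention serious, whatever its severity, so any SAE counts by arm would not be comparable

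*Protocol*

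**What the plan says.** The definition is in Protocol section 3.8, under Procedures: "Serious adverse events were defined as death or admission to hospital, events attributable to the intervention, or events that caused unwarranted distress to a participant". It offers three routes to seriousness: a fatal or hospitalised outcome, attribution to the intervention, and distress described as unwarranted. Neither the second nor the third carries a threshold or a measure.

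Section 1.2 describes what CBT patients may experience: "Besides, they may feel emotionally uncomfortable at times" and "They may cry, get upset or feel angry during a challenging session, or may also feel physically drained". That section rates the risk of CBT as small and says of the other arm: "There are no risks for subjects on placebo".

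Section 3.11 states the control arm's exposure: "the control group will be provided with The Knee Book (Ministry of Health, 2013) and not receive further intervention". Both arms receive the booklet and routine care. Only the experimental arm has CBT sessions.

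Two further statements bear on safety. The suspension rule reads: "This research study will be suspended if more than 30 percent of the participants in treatment group show unexpected adverse event". Symptoms are to be collected by a general enquiry that is not limited to one arm: "Participants will be asked for any discomfort symptoms along the study period".

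**The concern.** Seriousness and relatedness answer different questions. Seriousness concerns what happened to the patient. Relatedness concerns whether the treatment caused it. The second route in the definition lets the answer to the relatedness question settle seriousness, so a mild event becomes serious because it was caused by CBT.

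Two consequences follow. First, the definition conflicts with section 1.2, which presents session reactions as part of a small risk, while section 3.8 can place the same reactions beside death and admission. Second, the route is open in practice to one arm only. A table of SAEs by arm could show an excess on CBT that reflects the definition rather than any difference in deaths or admissions. The definition governs what is recorded from the first patient. If the form captures only that an event was an SAE, and not by which route, the routes cannot easily be separated afterwards.

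**Working it through.** The protocol gives no SAE rate, no SAE comparison and no figure to reproduce. The check is a reading of the sections side by side.

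1. **Structure of the definition (section 3.8, Procedures).** The routes are joined by 'or', so meeting one is enough. The attribution route needs only a causal judgement.

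2. **Could the wording be read more narrowly?** Suppose attribution was meant to qualify death or admission. A death judged unrelated would then fall outside the definition. Seriousness would still depend on attribution, so this reading does not cure the fault.

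3. **Applied to section 1.2.** That section describes tears, anger, upset and fatigue arising in sessions. If such a reaction is recorded as an event and judged due to CBT, the attribution route is met. This is a literal reading. The protocol does not say whether these reactions are to be recorded as adverse events at all.

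4. **Applied to the control arm (section 3.11).** Controls have no CBT sessions, so no event there can be attributed to CBT. Both arms receive the booklet. If 'the intervention' were taken to include it, a control event could in principle qualify, but the experimental arm would still have an additional source of attributable events. Section 3.9 names CBT as the main independent variable, which makes CBT the likelier meaning.

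5. **The distress route.** It is not tied to CBT and can be met in either arm. The word 'unwarranted' is undefined. It may well exclude distress that is expected in therapy. This route is vague, but it does not create the asymmetry.

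6. **Who judges attribution.** Section 3.8, under Randomization and Masking, says: "Because of the nature of the treatments, the participants or those providing the interventions to treatment assignment will be unable to mask". The protocol does not name who decides attribution. A judgement by the therapist or the participant would be made with the allocation known.

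7. **Direction of the effect.** Let b be the probability of death or admission, taken as equal in the two arms. Let r be the probability that a CBT patient has a session reaction classed as serious by attribution alone, taken as independent of b. Leaving the distress route aside:
   - control arm: P(SAE) = b
   - CBT arm: P(SAE) = 1 − (1 − b)(1 − r) = b + r(1 − b)
   - difference: r(1 − b), which is above zero whenever r > 0 and b < 1

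   The protocol gives neither b nor r, so only the direction can be stated. If the attribution route is removed, r no longer enters and the difference is zero.

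8. **What depends on the definition.** Section 3.9 lists knee pain as primary and functional and psychological measures as secondary, with no safety outcome. Section 3.13 names tests of outcomes and no adverse event comparison. The suspension rule counts unexpected adverse events in the treatment group, not SAEs. No stated analysis or decision rule uses the SAE definition.

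**The case against.** The strongest reply is that the definition triggers nothing in this document. No safety objective, hypothesis or outcome is stated, no comparison of SAEs is planned, and the suspension rule rests on a different category. That stands, and it limits the point to what is recorded and reported as an SAE.

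A reader might infer more from the definition in four ways, none of which the protocol supports:

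- **That a planned between-arm SAE comparison is biased.** None is stated. How SAEs would be tabulated may be set out in an analysis plan that is not at hand. The lack of comparability is conditional on counts by arm being reported.
- **That sites must log every tearful or angry moment as an SAE.** An SAE has first to be an adverse event. The examples of adverse events under Procedures are increased knee pain and emotional breakdown, and nothing classes the milder reactions in section 1.2 as adverse events. The wording allows this outcome on a literal reading but does not establish it.
- **That the distress route also captures expected reactions and loads them on one arm.** The qualifier may exclude them, and controls can meet this route too.
- **That the trial could not then say anything about the risk of CBT.** Death and admission are named separately in the definition and could still be counted by arm if the form records them.

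What the reply does not remove is the fault in the wording: relatedness alone suffices for seriousness, and this sits badly with section 1.2.

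**Conclusion.** The point holds as a fault in a stated rule. Section 3.8 uses causality as a criterion of seriousness with no severity threshold. Read literally, it can class the session reactions of section 1.2 with death and hospital admission. Because that criterion cannot be met through CBT in the control arm, any SAE counts given by arm would not be comparable.

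No size can be given, since the protocol contains no rate of session reactions, admissions or deaths. The direction, an excess on CBT, follows from the definition provided that at least some reactions are classed as serious by attribution alone and that 'the intervention' means CBT.

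The efficacy analyses, the sample size and the suspension rule are unaffected. The correction is worth making because it changes what is recorded as an SAE and costs almost nothing.

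**What to change.** In section 3.8, under Procedures:

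- define seriousness by criteria that do not depend on attribution and that apply identically in both arms;
- remove attribution to the intervention from the seriousness definition, and record relatedness as a separate field on the event form;
- either define the distress criterion so that it can be applied alike in both arms, or drop it.

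Reconcile sections 1.2 and 3.8 so that the protocol says how expected session reactions are classified. The choice of seriousness criteria, and of the class for those reactions, rests with the sponsor.

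The cost is protocol wording and one form field. No extra patients, staff or visits are needed.

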### **3.13 DATA ANALYSIS PLAN**

Data collected will be analyzed using Statistical Package for Social Sciences software (SPSS) version 21. Parametric tests (T-test, repeated measures ANOVA and correlation analysis) will be performed. P value for test of significance of results will be set at 0.05, alpha level (Type 1 error) at 0.05 (Confidence Interval of 95%). Analysis of outcomes will be by intention-to-treat where all participants who were randomized and entered the trial need to be included in the analysis in the condition to which they were assigned, regardless of whether they completed the trial, or may even have switched over to receive the incorrect treatment, per-protocol (complete case) analysis and chi square test.

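### Section 3.8 withdraws randomised patients from the study for a detected psychiatric disorder or pregnancy without providing for further outcome collection, which is not reconciled with the intention-to-treat analysis in 3.13

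*Protocol*

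**What the plan says.** Protocol section 3.8, under Procedures, gives two grounds for taking a patient out after randomisation. The first is that "the participants will be withdrawn from the study if any criminal illness detected which is non-identified psychiatric disorder". The wording is unclear; I read it as a psychiatric disorder not known at entry. The second is pregnancy, in a clause that begins "participants will be removed from the study if the female participant has". The paragraph adds: "The withdrawn participants will not be replaced in this study". Both rules speak of leaving the study, not of stopping the CBT sessions. The protocol does not say whether questionnaires are still collected afterwards.

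Section 3.13 describes the intention-to-treat analysis: "all participants who were randomized and entered the trial need to be included in the analysis in the condition to which they were assigned". It makes clear that this covers non-completers too, since it applies "regardless of whether they completed the trial". The same sentence lists a "per-protocol (complete case) analysis and chi square test". On methods it says: "Parametric tests (T-test, repeated measures ANOVA and correlation analysis) will be performed".

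Section 3.11 gives the CBT arm three group sessions of two and a half hours, "supervised by an experienced senior clinical psychologist" and a physiotherapist, and delivered by physiotherapists and nurses. Controls have routine care and the booklet. Section 3.1 puts both arms on the same assessment schedule.

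**The concern.** Section 3.8 takes patients out of the study and section 3.13 keeps them in the analysis. Both can hold only if outcomes are still collected after withdrawal, or if missing outcomes are filled in by some method. The protocol provides for neither. An analysis plan can choose a missing-data method, but it cannot recover questionnaires that were never given.

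The psychiatric ground needs most attention because it selects patients on something close to what H4 to H6 measure. Section 3.4 excludes only disorders already diagnosed, so undiagnosed patients can enter either arm and be found later. If they are found more often in one arm, the patients left in the two arms are no longer comparable on the distress outcomes.

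**Working it through.** **1. The two sections side by side**

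| Question | Section 3.8, Procedures | Section 3.13 |
|---|---|---|
| What the patient leaves | The study | Not addressed |
| Outcomes collected after withdrawal | Not stated | Not stated |
| Included in the analysis | Not stated | Yes, as assigned, completer or not |
| Method for absent outcomes | Not stated | None named |

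If follow-up stops, a withdrawn patient has a baseline record, because sections 3.8 and 3.12 place the questionnaire before CBT and before allocation, and perhaps some early visits. A repeated measures ANOVA in its standard form needs every visit, so it drops the patient. So does a complete-case analysis.

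**2. Opportunity for detection by arm**

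Contact added in the CBT arm: 3 sessions × 2.5 hours = 7.5 hours. Section 3.11 adds psychologist supervision and psychologist review of a random sample of recordings. Section 1.2 expects sessions to bring out painful emotions. Shared by both arms: the questionnaires, their schedule, and routine clinic and physiotherapy visits. No section makes a questionnaire score a trigger for withdrawal, and no detection procedure or rate by arm is given.

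**3. The plan's depression figures**

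Section 3.5(c): SD 5.83; planned difference 12.06 − 9.65 = 2.41.

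n per group = 2 × 5.83² × (1.96 + 0.842)² / 2.41² = 91.9, rounded up to 92. This agrees with the stated 92, so these figures can serve as a scale.

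**4. Illustration: unadjusted follow-up mean**

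Assumptions, none of them from the protocol: an excess fraction f of the CBT arm is removed, nobody is removed from the control arm, and removed patients would score k SD above their arm's mean. The mean of those remaining falls by f × k / (1 − f) SD.

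For f = 0.05 and k = 1.5: 0.05 × 1.5 / 0.95 = 0.079 SD; × 5.83 = 0.46 points; 0.46 / 2.41 = 19% of the planned difference.

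| Excess removed, f | Shift in points, k = 1 to 2 | Share of 2.41 |
|---|---|---|
| 1% | 0.06 to 0.12 | 2% to 5% |
| 2% | 0.12 to 0.24 | 5% to 10% |
| 5% | 0.31 to 0.61 | 13% to 25% |
| 10% | 0.65 to 1.30 | 27% to 54% |

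In this comparison the shift favours CBT.

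**5. Illustration: change from baseline**

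In a complete-case repeated measures analysis the removed patient's baseline drops out too. If that patient is b SD above the mean at baseline and k SD above it at follow-up, the shift in mean change is f × (k − b) / (1 − f).

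- b = k = 1.5: no shift.
- b = 1, k = 1.5, f = 0.05: 0.05 × 0.5 / 0.95 = 0.026 SD, or 0.15 points, in favour of CBT.
- b = 1.5, k = 1, f = 0.05: the same 0.15 points, against CBT. This is what regression to the mean would give.

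So neither the size nor the direction is fixed until the analysis is.

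**6. Pregnancy**

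Nothing in the protocol suggests that pregnancy occurs or is detected at different rates by arm, and eligible patients are 35 to 75 years old. The expected shift between arms is nil.

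**The case against.** The strongest objection is that the two sections do not contradict each other. Section 3.8 does not say that withdrawn patients leave the analysis, and section 3.13 includes non-completers in express terms. How absent values are handled is commonly left to an analysis plan, and none was available to this review. This stands as far as it goes: a reader might infer a proven contradiction, and the text supports only an unreconciled tension. It does not dispose of the point, because whether outcomes are collected after withdrawal is a matter for the protocol.

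A reader might also infer that detection is far likelier under CBT, or that the rule in effect acts on one arm. The documents do not support that. The rule is worded for all participants, and both arms complete the same questionnaires on the same schedule. The sessions are delivered in groups by physiotherapists and nurses, with no psychiatric assessment in the listed content. What remains is a reasonable inference from the added contact.

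It is tempting to go further and say that distress, and with it pain, is biased towards CBT. The removal rates above are assumed, zero removals among controls is the extreme case, and the direction can reverse under a change analysis. Section 3.9 makes knee pain the primary outcome and lists depression and anxiety as secondary; an effect on pain would be conjecture. The bias argument does not extend to pregnancy at all.

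**Conclusion.** The point holds in a limited form and is worth correcting. Section 3.8 withdraws randomised patients from the study on two grounds without providing for later outcomes, and section 3.13 requires an analysis that observed data could not then supply. The psychiatric ground adds a risk of informative loss for H4 to H6. Its size is unknown: on the assumptions shown, from trivial at 1% excess removal, through 0.46 points at 5% and 1.5 SD, to 1.30 points at 10% and 2 SD, against a planned 2.41. These figures apply only to an unadjusted follow-up comparison with no control removals. Under a complete-case repeated measures analysis the shift may be nil or go either way. Pregnancy is an intention-to-treat matter only. Confidence is medium: the gap between the sections is plain, but the difference in detection is inferred.

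**What to change.** Reconcile section 3.8 with section 3.13 by separating two events: stopping the CBT sessions and leaving the study. Whether a patient stops the sessions stays a clinical decision for the investigator, and nothing here proposes a rule for it. State that a patient who stops keeps completing the questionnaires at all three follow-ups (immediately, one month and six months after the intervention) unless consent is withdrawn, and is analysed in the randomised arm. Report the reasons for stopping by arm, so that any imbalance can be seen. Reword the psychiatric ground so that its meaning is clear.

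The cost is a sentence or two in the protocol and the consent form, a few more questionnaires, and continued contact with patients who have stopped the sessions.
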